Appendix 1. Protocol JNBA mTPI and Simulation

The modified toxicity probability interval (mTPI) method employs a simple beta-binomial hierarchical model. Decision rules are based on calculating the unit probability mass (UPM) of 3 intervals corresponding to under dosing, proper dosing, and over dosing in terms of toxicity. Specifically, the under dosing interval is defined as $(0, p_T - \varepsilon_1)$, the overdosing interval as $(p_T + \varepsilon_2, 1)$, and the proper dosing interval as $(p_T - \varepsilon_1, p_T + \varepsilon_2)$, where ε_1 and ε_2 are small fractions, such as 0.05, to account for the uncertainty around the true target toxicity. A sensitivity analysis reported by Ji et al. (2010) showed that the mTPI design is robust to the specification of ε values.

In addition, ε_1 and ε_2 could take different values to reflect physician preference and the nature of the disease. For advanced diseases with few treatment options, higher toxicity rates might be considered acceptable, implying a specification of $\varepsilon_2 > \varepsilon_1$. For less advanced diseases, the 2 ε values could be identical or ε_1 could be $> \varepsilon_2$. The 3 dosing intervals are associated with 3 different dose-escalation decisions. The under-dosing interval corresponds to a dose escalation (E), overdosing corresponds to a dose de-escalation (D), and proper dosing corresponds to staying at the current dose (S).

Given an interval and a probability distribution, the UPM of that interval is defined as the probability of the interval divided by the length of the interval. The mTPI design calculates the UPMs for the three dosing intervals, and the one with the largest UPM implies the corresponding dose-finding decision. That decision provides the dose level to be used for future patients. For example, if the under dosing interval has the largest UPM, decision E, to escalate, will be executed, and the next cohort of patients will be treated at the next-higher dose level. Ji et al. (2010) show that the decision based on the UPM is optimal in that it minimizes a subsequent expected loss. Under the mTPI design, a trial is terminated when either the lowest dose is above the maximum tolerated dose (MTD) or a pre-specified maximum sample size is reached.

Simulation

A small simulation study was conducted to compare the mTPI with 3+3 in identifying the right MTD. Six scenarios were run, each with 1000 simulated trials. As in Study JNBA, the MTD has a target toxicity probability of $P_T = 0.3$ and ε_1 and ε_2 are set at 0.013 and 0.001 respectively. The scenarios assumed the true probabilities of six doses as follows: scenario 1 = (0.1, 0.2, 0.3, 0.4, 0.5, 0.6); scenario 2 = (0.08, 0.16, 0.24, 0.3, 0.38, 0.46); scenario 3 = (0.04, 0.08, 0.12, 0.16, 0.2, 0.24); scenario 4 = (0.4, 0.5, 0.6, 0.7, 0.8, 0.9); scenario 5 = (0.04, 0.08, 0.12, 0.16, 0.2, 0.58); and scenario 6 = (0.06, 0.46, 0.53, 0.6, 0.67, 0.74). For all scenarios, the probability of selecting each dose was summarized, the average number of patients treated at each dose and average number of patients experience DLT at each dose. The simulation demonstrates that, in general, mTPI method correctly identifies the MTD more than 3+3 and appears to be as safe as 3+3 method in that it puts a similar percentage of patients on toxic doses.

Scenario	Dose Level	True Prob (tox)	Selection Prob (%)		# of Subjects Treated		# of Toxicities	
			mTPI	3+3	mTPI	3+3	mTPI	3+3
1	1	0.1	4.3	31.5	5.583	4.473	0.534	0.42
	2	0.2	29.5	33.2	10.02	4.617	1.985	0.979
	3	0.3	42.7	19.5	9.306	3.15	2.811	0.983
	4	0.4	18.4	5.7	4.023	1.371	1.624	0.57
	5	0.5	4.5	0.7	0.9	0.381	0.442	0.194
	6	0.6	0.4	0	0.114	0.048	0.07	0.029
2	1	0.08	1.1	21.1	4.5	4.083	0.339	0.295
	2	0.16	15.7	30.6	8.082	4.494	1.237	0.735
	3	0.24	33.1	23	8.832	3.642	2.125	0.902
	4	0.3	31.3	14	5.601	2.28	1.659	0.692
	5	0.38	14.2	4.3	2.325	1.083	0.886	0.409
	6	0.46	4.6	0.1	0.66	0.297	0.305	0.141
3	1	0.04	0	7.1	3.561	3.51	0.146	0.139
	2	0.08	1.7	10.9	4.626	3.81	0.375	0.315
	3	0.12	8.1	16	5.811	3.918	0.743	0.45
	4	0.16	19.1	20.8	6.045	3.723	0.953	0.578
	5	0.2	24.4	14.5	4.776	3.132	0.934	0.654
	6	0.24	46.7	1.2	5.181	1.908	1.251	0.451
4	1	0.4	46.5	22.2	18.318	4.914	7.374	1.931
	2	0.5	5.4	3.1	3.276	1.434	1.64	0.721
	3	0.6	0.5	0	0.408	0.228	0.253	0.139
	4	0.7	0	0	0.021	0.018	0.014	0.012
	5	0.8	0	0	0.003	0	0.003	0
	6	0.9	0	0	0	0	0	0
5	1	0.04	0.4	6.8	3.648	3.51	0.155	0.146
	2	0.08	1.3	11.6	4.398	3.834	0.354	0.314
	3	0.12	6.3	16.7	5.613	3.909	0.657	0.448
	4	0.16	21	20.7	6.171	3.669	0.998	0.604
	5	0.2	55.8	37.6	6.813	3.594	1.32	0.729
	6	0.58	15.2	0.8	3.357	1.788	1.936	1.038
6	1	0.06	59.3	80.9	13.71	5.556	0.809	0.314
	2	0.46	36.7	13.5	13.98	4.461	6.513	2.038
	3	0.53	3.7	1.5	2.067	0.858	1.098	0.481
	4	0.6	0.1	0	0.195	0.102	0.114	0.064

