At a dose of 1000 mg, the mean terminal elimination-life ($t_{1/2}$) is approximately 100 hours (approximately 4 days). As a result, the administration of LY3164530 every 2 weeks may not be the optimal schedule of administration in order to achieve a LY3164530 $C_{min,\tau}$ near the MET EC_{50} . Therefore, it is hypothesized that weekly dosing of LY3164530 (ie, Days 1, 8, 15, and 22 of a 28 day cycle) will minimize the fluctuation between the peak (C_{max}) and trough ($C_{min,\tau}$) serum concentrations of LY3164530 leading to a more consistent inhibition of both MET and EGFR over the dosing interval (with minimal impact on the accumulation of LY3164530) and potentially greater pharmacologic activity (PD response). The MTD of LY3164530 when administered on Days 1 and 15 of a 28 day cycle is 1000 mg. As a result, the starting dose for the weekly schedule will be 500 mg. The safety, toxicity, PK, and PD associated with a weekly schedule will be assessed.

6. Investigational Plan

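### SAP Appendix 1 leaves nearly all top-dose clearances out of the 3+3 selection column, and neither document defines the right MTD, so two exceptions to the stated mTPI advantage go unmentioned

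*SAP*

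**What the plan says.** SAP Appendix 1 compares mTPI with 3+3 by simulation: "Six scenarios were run, each with 1000 simulated trials". The target DLT rate is 0.30, with epsilon values of 0.013 below and 0.001 above. Six doses are simulated, and the table prints for each design the percentage of trials selecting each dose, with the mean patients and mean toxicities per dose. The text concludes: "The simulation demonstrates that, in general, mTPI method correctly identifies the MTD more than 3+3".

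Three things are not stated:

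- how a 3+3 trial that clears dose 6 is counted;
- how often no dose is selected;
- which dose is the right MTD when none has a true rate of 0.30, as in scenarios 3 to 6.

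The nearest the appendix comes to the last point is its stopping rule, "Under the mTPI design, a trial is terminated when either the lowest dose is above the maximum tolerated dose (MTD"), or when a maximum sample size is reached, together with an overdosing interval that starts just above target.

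Protocol Attachment 7 carries the same scenarios and the same concluding sentence, but a different table of results.

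**The concern.** In scenario 3 every dose is below target, so dose 6 is the best available. The SAP credits mTPI with choosing it in 46.7% of trials and 3+3 in 1.2%. The mTPI column adds to 100.0% and the 3+3 column to 70.5%. With a true rate of 0.04 at dose 1, stopping with no dose cannot explain a gap of 29.5 points. If the gap is trials that cleared the top dose, the two designs were scored by different rules in the scenario where that matters most.

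The second worry is the conclusion itself. In scenario 4 all doses are above target, and in scenario 6 all but the first are. In both, mTPI names an above-target dose more often than 3+3. Whether that counts against mTPI depends on a definition that the text does not give. At stake is the accuracy of the operating characteristics that the plan reports for its chosen design.

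**Working it through.** **Inputs.** True DLT rates and printed results come from SAP Appendix 1 and Protocol Attachment 7. The 3+3 rule assumed is the standard one: cohorts of 3, expand to 6 on 1 of 3, escalate on 0 of 3 or at most 1 of 6, and stop when dose 6 is cleared.

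**Step 1: printed totals, SAP scenario 3.**

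- 3+3: 7.1 + 10.9 + 16 + 20.8 + 14.5 + 1.2 = 70.5, leaving 29.5 unallocated.
- mTPI: 0 + 1.7 + 8.1 + 19.1 + 24.4 + 46.7 = 100.0.

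**Step 2: exact 3+3 probabilities at dose 6, scenario 3.** With p the true rate and q = 1 − p, P(clear a dose) = q³ + 3pq² × q³.

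- P(reach dose 6) = 0.983 × 0.937 × 0.871 × 0.793 × 0.709 = 0.451.
- At p = 0.24, q³ = 0.4390 and 3pq² = 0.4159.
- Expected patients at dose 6 = 0.451 × (3 + 3 × 0.416) = 1.916 (printed 1.908).
- Expected toxicities = 1.916 × 0.24 = 0.460 (printed 0.451).
- P(clear dose 6 once reached) = 0.4390 + 0.4159 × 0.4390 = 0.6215.
- P(clear dose 6) = 0.451 × 0.6215 = 0.280, so **28.0%** (printed 1.2%).

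The simulated trials therefore reached dose 6 as often as they should. Only the selection entry is off.

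**Step 3: the other cells.** A 60,000-trial simulation, filling the lower dose to 6 after de-escalation, gives 6.3, 12.3, 17.1, 18.5 and 15.6% for doses 1 to 5. Their total is 70.0% before rounding; the printed total is 69.3%. No dose was selected in 1.8% and dose 6 was cleared in 28.2%. From the table alone, 29.5 − 1.8 + 1.2 = 28.9%.

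**Step 4: could it be chance?** With 1000 trials the standard error at 28% is √(0.28 × 0.72 / 1000) = 1.42 points, and (28.0 − 1.2) / 1.42 is about 19 standard errors.

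**Step 5: sensitivity to the 3+3 variant.** Without filling the lower dose after de-escalation, 28.0% still clear dose 6. Requiring 6 patients at the top dose gives 25.3%, but implies 2.53 patients there, which does not match the printed 1.908.

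**Step 6: the other affected scenarios.**

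| SAP scenario | P(reach dose 6) | P(clear once reached) | Expected at dose 6 | Printed |
|---|---|---|---|---|
| 3 | 0.451 | 0.6215 | 28.0% | 1.2% |
| 5 | 0.451 | 0.0968 | 4.4% | 0.8% |
| 2 | 0.0783 | 0.2208 | 1.7% | 0.1% |

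Attachment 7 prints 25.4%, 3.7% and 1.6% for these cells.

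**Step 7: effect on the comparison.** The scenario 3 lead of mTPI in the SAP is 46.7 − 1.2 = 45.5 points as printed and 46.7 − 28.0 = 18.7 points when rescored.

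**Step 8: correct selection if the MTD is the highest dose at or below 30%, or no dose if none qualifies.** The scenario 4 entries are the shares allotted to no dose. SAP: 100 − 52.4 = 47.6 and 100 − 25.3 = 74.7. Attachment 7: 100 − 55.0 = 45.0 and 100 − 17.2 = 82.8.

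| Scenario | Correct answer | SAP, mTPI vs 3+3 (%) | Attachment 7, mTPI vs 3+3 (%) |
|---|---|---|---|
| 1 | dose 3 | 42.7 vs 19.5 | 35.1 vs 19.4 |
| 2 | dose 4 | 31.3 vs 14.0 | 29.2 vs 10.8 |
| 3 | dose 6 | 46.7 vs about 28 (rescored) | 70.8 vs 25.4 |
| 4 | no dose | 47.6 vs 74.7 | 45.0 vs 82.8 |
| 5 | dose 5 | 55.8 vs 37.6 | 75.7 vs 24.6 |
| 6 | dose 1 | 59.3 vs 80.9 | 60.4 vs 76.8 |

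**Step 9: the alternative definition, the dose closest to 30%.** In scenario 4 this is dose 1 (SAP: 46.5 vs 22.2). In scenario 6 it is dose 2, because |0.46 − 0.30| = 0.16 is less than |0.06 − 0.30| = 0.24 (SAP: 36.7 vs 13.5). mTPI then leads in both.

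**The case against.** **The top dose.** One could say that a 3+3 trial clearing the top dose has not found an MTD and should be credited with none. That convention would give 0% at dose 6, not 1.2%. It is also not applied to mTPI, whose column adds to 100.0%, and Attachment 7 does credit such trials. What stands is that nearly all clearances are missing, not all.

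**The conclusion.** A reader might infer that scenarios 4 and 6 contradict the concluding sentence. The documents do not support that. The sentence is qualified by *in general*, mTPI leads in four of six scenarios even after rescoring, and under the closest-to-30% reading it leads in scenarios 4 and 6 as well. Against that reading, it counts doses of 0.40 and 0.46 as right, although the appendix's overdosing interval begins at 0.30 + 0.001 = 0.301. The stopping rule also points to no dose in scenario 4, but it does not settle scenario 6. The supportable criticism is an undefined term and two undisclosed exceptions.

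**The protocol.** A reader might carry the scoring fault over to Attachment 7. Its scenario 3 lead, 70.8 − 25.4 = 45.4 points, already counts top-dose clearances.

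**The case for mTPI.** A reader might take this table as the sole support for the design. Protocol Section 7.2.2.3 and SAP Section 6.13 also argue from the conservatism of 3+3 and cite published work.

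**The weekly schedule.** A reader might link scenarios 4 and 6 to Schedule 2, because 4 × 500 mg and 2 × 1000 mg both total 2000 mg per 28 days. That toxicity follows the 28-day total is not stated. If it did, the first weekly dose would match the stated Schedule 1 MTD. Scenario 4, which starts at 0.40, and scenario 6, which goes from 0.06 to 0.46, do not represent that.

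**Conclusion.** The scoring fault is established for the SAP table. Scenario 3, dose 6 should read about 28% for 3+3 instead of 1.2%, so the lead of mTPI there is about 19 points, not 45.5. The errors in scenario 5 (0.8% printed, about 4.4% expected) and scenario 2 (0.1%, about 1.7%) are small, concern doses above target, and do not alter the correct-selection rates. This rests on the standard 3+3 rule, which the table's patient and toxicity counts at dose 6 bear out.

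The second finding is conditional. With the MTD defined as the highest dose at or below 30%, or none, the SAP shows mTPI correct less often by 74.7 − 47.6 = 27.1 points in scenario 4 and 80.9 − 59.3 = 21.6 points in scenario 6. Attachment 7 shows the same direction (37.8 and 16.4 points). The scenario 4 figures read the unallocated share as no dose selected. A simulated 3+3 gives 75.8% against the SAP's 74.7%, but neither table prints that row, and the 3+3 column in Attachment 7 has unallocated shares in other scenarios that its text does not explain.

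The general statement survives in four scenarios. No escalation rule or RP2D criterion is affected.

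**What to change.** In SAP Appendix 1, rescore the 3+3 column so that clearing dose 6 counts as selecting dose 6 (about 28% in scenario 3, 4.4% in scenario 5 and 1.7% in scenario 2; the exact values should come from the stored runs). Add a row for no dose selected, so that each column totals 100%.

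In both documents, define the correct MTD for each scenario; the highest dose with a true DLT rate at or below 30%, or no dose if none qualifies, fits the appendix's own intervals. Then replace the concluding comparison with a statement such as: under this definition mTPI is correct more often than 3+3 in scenarios 1, 2, 3 and 5 and less often in scenarios 4 and 6. Each document should quote its own table:

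- SAP: 47.6% vs 74.7% (scenario 4) and 59.3% vs 80.9% (scenario 6).
- Attachment 7: 45.0% vs 82.8% and 60.4% vs 76.8%.

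The cost is rescoring an existing simulation and rewording one sentence in two places. The downside is a less favourable stated advantage for mTPI. Trial conduct does not change.
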